9.1.2 Form

Nivolumab Injection is a clear to opalescent, colorless to pale yellow liquid; light (few) particulates may be present. The drug product is a sterile, non-pyrogenic, single-use, isotonic aqueous solution formulated in sodium citrate, sodium chloride, mannitol, diethylenetriamine pentacetic acid (pentetic acid) and polysorbate 80 (Tween® 80), pH 6.0.

Nivolumab is supplied by Bristol-Myers Squibb and distributed as 100 mg vials (10 mg/mL) with a 0.7 mL overfill. It is supplied in 10 mL type I flint glass vials, with butyl rubber stoppers and aluminum seals.

9.1.3 Storage and stability

Nivolumab Injection, 100 mg/10 mL (10 mg/mL) vials of nivolumab injection must be stored at 2°C to 8°C (36°F to 46°F) and protected from light and freezing.

Undiluted Nivolumab Injection and Diluted Nivolumab Injection in the IV Container

BrUOG 355: 7/8/17, 7/11/17, 7/20/17, 8/7/17, 8/8/17, 8/14/17, 8/16/17, 8/21/17, 8/22/17, 8/24/17, 8/28/17, 9/5/17, 9/6/17, 9/8/17, 9/11/17, 11/7/17, 11/8/17, 11/19/17 approved DD, 11/20/17, 12/12/17, 12/14/17, 1/29/18, 2/1/18, 2/6/18, 2/7/18, 2/8/18, 2/9/18, 2/12/18, 2/13/18, 3/8/18 all reviews, 3/9/18, 3/13/18, 3/14/18, 3/15/18, 4/19/18, 4/23/18, 5/29/18, 6/5/18, Amendment # 1 7/9/18, Amendment # 2 12/12/18, Amendment #3, 4/6/2020, Amendment #4 5/11/2020

The administration of nivolumab infusion must be completed within 24 hours of preparation. If not used immediately, the infusion solution may be stored under refrigeration conditions (2°C to 8°C, 36°F to 46°F) for up to 24 hours, and a maximum of 8 hours of the total 24 hours can be at room temperature (20°C to 25°C, 68°F to 77°F) and room light. The maximum of 8 hours under room temperature and room light conditions includes the product administration period.

Shelf life

Unopened vial 2 years.

After opening:

From a microbiological point of view, once opened, the medicinal product should be infused or diluted and infused immediately.

After preparation of infusion

From a microbiological point of view, the product should be used immediately.

If not used immediately, chemical and physical in-use stability of OPDIVO has been demonstrated for 24 hours at 2°C to 8°C protected from light and a maximum of 8 hours at 20°C-25°C and room light (this 8-hour period of the total 24 hours should be inclusive of the product administration

9.1.4 Compatibility

No incompatibilities between Nivolumab injection and polyvinyl chloride (PVC), non-PVC/non-DEHP (di[2-ethylhexyl]phthalate) IV components, or glass bottles have been observed.

9.1.5 Handling

Qualified personnel, familiar with procedures that minimize undue exposure to themselves and the environment, should undertake the preparation, handling, and safe disposal of the chemotherapeutic agent in a self-contained and protective environment.

9.1.6 Availability

Nivolumab is an investigational agent and will be supplied free of charge from Bristol-Myers Squibb.

9.1.7 Preparation

Visually inspect the drug product solution for particulate matter and discoloration prior to administration. Discard if solution is cloudy, if there is pronounced discoloration (solution may have a pale-yellow color), or if there is foreign particulate matter other than a few translucent-to-white, amorphous particles.

*Note: Mix by **gently** inverting several times. **Do not** shake.*

Aseptically withdraw the required volume of nivolumab solution into a syringe, and dispense into an IV bag. If multiple vials are needed for a subject, it is important to use a separate sterile syringe and needle for each vial to prevent problems such as dulling of needle tip, stopper coring,

BrUOG 355: 7/8/17, 7/11/17, 7/20/17, 8/7/17, 8/8/17, 8/14/17, 8/16/17, 8/21/17, 8/22/17, 8/24/17, 8/28/17, 9/5/17, 9/6/17, 9/8/17, 9/11/17, 11/7/17, 11/8/17, 11/19/17 approved DD, 11/20/17, 12/12/17, 12/14/17, 1/29/18, 2/1/18, 2/6/18, 2/7/18, 2/8/18, 2/9/18, 2/12/18, 2/13/18, 3/8/18 all reviews, 3/9/18, 3/13/18, 3/14/18, 3/15/18, 4/19/18, 4/23/18, 5/29/18, 6/5/18, Amendment # 1 7/9/18, Amendment # 2 12/12/18, Amendment #3, 4/6/2020, Amendment #4 5/11/2020

repeated friction of plunger against syringe barrel wall. **Do not** enter into each vial more than once. **Do not** administer study drug as an IV push or bolus injection

Add the appropriate volume of 0.9% Sodium Chloride Injection solution or 5% Dextrose Injection solution. *It is acceptable to add nivolumab solution from the vials into an appropriate pre-filled bag of diluent.*

Note: Nivolumab infusion concentration must be at or above the minimum allowable concentration of 0.35 mg/mL (see most up to date IB for reference)

Note: It is not recommended that so-called “channel” or tube systems are used to transport prepared infusions of nivolumab.

Attach the IV bag containing the nivolumab solution to the infusion set and filter.

At the end of the infusion period, flush the line with a sufficient quantity of approved diluents. After nivolumab (BMS-936558-01) has been prepared for administration, the total storage time (combination of refrigeration and room temperature) is not to exceed 24 hours

Please refer to the current Investigator Brochure. Due to parameters surrounding the use time of nivolumab, the time of preparation should be noted in the Pharmacy Source documents [accountability logs] or in study files as required for investigator sponsored research [FDA and GCP].

9.1.8 Administration

The administration of BMS-936558-01 injection prepared for dosing nivolumab infusion must be completed within 24 hours of preparation. If not used immediately, the infusion solution may be stored under refrigeration conditions (2°C to 8°C, 36°F to 46°F) for up to 24 hours, and a maximum of 8 hours of the total 24 hours can be at room temperature (20°C to 25°C, 68°F to 77°F) and room light. The maximum of 8 hours under room temperature and room light conditions includes the product administration period.

Nivolumab will be given every two weeks at a dose of 240 mg to be administered as a 30 minute IV infusion. In maintenance the dose is 480mg to be administered as per the Investigator Brochure as a 30 minute IV infusion.

When the dose is fixed (eg, 240 mg, 360 mg, or 480 mg flat dose), nivolumab injection can be infused undiluted or diluted so as not to exceed a total infusion volume of 160 mL.

There are no premedications recommended for nivolumab on the first cycle. There will be no dose modifications allowed.

Subjects should be carefully monitored for infusion reactions during nivolumab administration. If an acute infusion reaction is noted, subjects should be managed according to the Protocol.

BrUOG 355: 7/8/17, 7/11/17, 7/20/17, 8/7/17, 8/8/17, 8/14/17, 8/16/17, 8/21/17, 8/22/17, 8/24/17, 8/28/17, 9/5/17, 9/6/17, 9/8/17, 9/11/17, 11/7/17, 11/8/17, 11/19/17 approved DD, 11/20/17, 12/12/17, 12/14/17, 1/29/18, 2/1/18, 2/6/18, 2/7/18, 2/8/18, 2/9/18, 2/12/18, 2/13/18, 3/8/18 all reviews, 3/9/18, 3/13/18, 3/14/18, 3/15/18, 4/19/18, 4/23/18, 5/29/18, 6/5/18, Amendment # 1 7/9/18, Amendment # 2 12/12/18, Amendment #3, 4/6/2020, Amendment #4 5/11/2020

Doses of nivolumab may be interrupted, delayed, or discontinued depending on how well the subject tolerates the treatment.

Nivolumab Injection, 100 mg/10 mL (10 mg/mL)

Nivolumab injection is to be administered as an IV infusion through a 0.2-micron to 1.2-micron pore size, low-protein binding polyethersulfone membrane in-line filter at the protocol-specified doses and infusion time. It is not to be administered as an IV push or bolus injection. Nivolumab injection can be infused undiluted (10 mg/mL) or diluted with 0.9% Sodium Chloride Injection, USP or 5% Dextrose Injection, USP to protein concentrations as low as 0.35 mg/mL. Care must be taken to assure sterility of the prepared solution as the product does not contain any antimicrobial preservative or bacteriostatic agent. No incompatibilities between nivolumab and polyvinyl chloride (PVC), non-PVC/non-DEHP (di(2-ethylhexyl) phthalate) IV components, or glass bottles have been observed.

9.1.9 Ordering

It is possible that sites may have more than one clinical study on the same drug ongoing at the same time. It is imperative that only drug product designated for this protocol be used for this study

If concerns regarding the quality or appearance of the investigational product arise, do not dispense the investigational product, and contact BMS immediately.

Please allow for 5-7 business days for the shipment of drug.

Initial Orders

- Following submission and approval of the required regulatory documents, BrUOG will activate each site, which will allow a supply of nivolumab (when applicable) to be ordered by the investigational pharmacist via the BrUOG 355 drug order form.
- It is required that the box “request for initial drug supply” be checked, the investigator address be confirmed as correct (if pre-populated) or populated (if blank), and that the # of vials being requested be documented on the form.
- Once complete, email the form to the email addresses on the drug order form: [contact] and Cc [contact].
- Nivolumab:
 - Nivolumab will be supplied in 100 mg vials.
 - The initial order should be limited to 20 vials. Allow 5 business days for shipment of drug from BMS receipt of the Drug Request Form. Drug is protocol specific, but not patient specific. All drug product will be shipped by courier in a temperature-controlled container. It is possible that sites may have more than one nivolumab clinical study ongoing at the same time. It is imperative that only drug product designated for this protocol number be used for this study.

BrUOG 355: 7/8/17, 7/11/17, 7/20/17, 8/7/17, 8/8/17, 8/14/17, 8/16/17, 8/21/17, 8/22/17, 8/24/17, 8/28/17, 9/5/17, 9/6/17, 9/8/17, 9/11/17, 11/7/17, 11/8/17, 11/19/17 approved DD, 11/20/17, 12/12/17, 12/14/17, 1/29/18, 2/1/18, 2/6/18, 2/7/18, 2/8/18, 2/9/18, 2/12/18, 2/13/18, 3/8/18 all reviews, 3/9/18, 3/13/18, 3/14/18, 3/15/18, 4/19/18, 4/23/18, 5/29/18, 6/5/18, Amendment # 1 7/9/18, Amendment # 2 12/12/18, Amendment #3, 4/6/2020, Amendment #4 5/11/2020

- When drug is received, it is required that an email be sent to [contact] to alert BrUOG the order was received.
- Take note that drug should be transferred to +2°C/+8°C storage immediately upon receipt
- Pharmacy supplies not provided by BMS: Empty IV bags/containers, approved diluents, In-line filters and infusion tubing

Re-Supply

- Drug re-supply request should be requested using the BrUOG 355 drug order form and allowing for 5-7 business days for drug shipment. Deliveries will be made Tuesday through Friday.
- When assessing need for resupply, institutions should keep in mind the number of vials used per treatment dose. Drug is not patient-specific. Be sure to check with your pharmacy regarding existing investigational stock to assure optimal use of drug on hand.
- It is required that the box “request for resupply” be checked, the investigator address be confirmed as correct (if pre-populated) or populated (if blank), and that the # of vials being requested be documented on the form.
- Once complete, email the form to the email addresses on the drug order form: [contact] and Cc [contact].
- When drug is ordered it is required that an email be sent to [contact] to alert BrUOG to the placed order.
- When drug is received, it is required that an email be sent to [contact] to alert BrUOG the order was received.

Drug Excursions

- Drug excursions should be reported immediately to BMS on the form provided with the study-specific drug order form. Please cc [contact] on all drug excursion emails

Questions on drug expiration, delayed shipments etc:

- Send an email to [contact] and cc [contact], [contact], and [contact]
- For questions on drug destruction please refer to 9.1.11 as this needs to be communicated directly with BrUOG only

9.1.10 Accountability

The investigator, or a responsible party designated by the investigator, should maintain a careful record of the inventory and disposition of the agent using the NCI Drug Accountability Record Form (DARF) or another comparable drug accountability form. (See the NCI Investigator’s Handbook for Procedures for Drug Accountability and Storage.)

9.1.11 Destruction and Return

At the end of the study, unused supplies of nivolumab will be destroyed according to institutional policies once BrUOG confirms and approves destruction. BrUOG will obtain approval to destroy

BrUOG 355: 7/8/17, 7/11/17, 7/20/17, 8/7/17, 8/8/17, 8/14/17, 8/16/17, 8/21/17, 8/22/17, 8/24/17, 8/28/17, 9/5/17, 9/6/17, 9/8/17, 9/11/17, 11/7/17, 11/8/17, 11/19/17 approved DD, 11/20/17, 12/12/17, 12/14/17, 1/29/18, 2/1/18, 2/6/18, 2/7/18, 2/8/18, 2/9/18, 2/12/18, 2/13/18, 3/8/18 all reviews, 3/9/18, 3/13/18, 3/14/18, 3/15/18, 4/19/18, 4/23/18, 5/29/18, 6/5/18, Amendment # 1 7/9/18, Amendment # 2 12/12/18, Amendment #3, 4/6/2020, Amendment #4 5/11/2020

from BMS. Destruction will be documented in the Drug Accountability Record Form and the form will be routed to BrUOG.

Each participating hospital and pharmacy must submit, up front and throughout the trial, the most up to date drug destruction policy, to BrUOG.

Drug that is used (partially used vial for examples), can be destroyed in real-time as per the pharmacy destruction policy and do not need to be tracked on the accountability log.

Expired drug: Contact BrUOG to provide the number of expired vials and the current accountability logs. BrUOG will obtain approval to destroy drug and will communicate approval the pharmacy. BrUOG will then require submission of the drug accountability log, documenting the drug destruction of expired material.

10 BIOMARKER, CORRELATIVE, AND SPECIAL STUDIES

The aim of such studies will be to identify potentially predictive biomarkers of benefit for patients with cervical cancer treated with nivolumab and standard chemoradiation. Data from these investigations will be evaluated for associations with response, survival (OS, PFS) and/or safety (adverse event) data. Biomarkers analysis may include PD-L1 expression, and tumor mutation burden. We may explore the prognostic significance of Chitinase 3-like 1 (Chi3l1), which we have recently demonstrated to have prognostic significance following immune checkpoint inhibitors in lung cancer. It is anticipated that advances in the understanding of biomarkers for immune checkpoint inhibitors will be forthcoming over the next few years emphasizing the need for tissue storage for future collaborative studies.

Tissue:

Diagnostic:

For patients with diagnostic tissue at Rhode Island Hospital, The Miriam Hospital or Women and Infants Hospital, tissue should remain in the Pathology Department until correlative testing is imminent. At that time, all patient's tissue will be requested for sectioning (20 unstained slides of 4uM thickness) or a FFPE.

For patients with diagnostic tissue outside of the system (defined above): Tissue will be requested from patient's baseline diagnostic sample or most recent biopsy. Samples are to be labeled with study number (BrUOG 355), patient initials, patient study number and time point.

Formalin-fixed paraffin embedded (FFPE) tumor tissue block or at least 20 unstained slides (charged) of 4 uM thickness will be required to be sent to the Clinical Research Center (CRC) at Rhode Island Hospital.

Lifespan Clinical Research Center
[name],

BrUOG 355: 7/8/17, 7/11/17, 7/20/17, 8/7/17, 8/8/17, 8/14/17, 8/16/17, 8/21/17, 8/22/17, 8/24/17, 8/28/17, 9/5/17, 9/6/17, 9/8/17, 9/11/17, 11/7/17, 11/8/17, 11/19/17 approved DD, 11/20/17, 12/12/17, 12/14/17, 1/29/18, 2/1/18, 2/6/18, 2/7/18, 2/8/18, 2/9/18, 2/12/18, 2/13/18, 3/8/18 all reviews, 3/9/18, 3/13/18, 3/14/18, 3/15/18, 4/19/18, 4/23/18, 5/29/18, 6/5/18, Amendment # 1 7/9/18, Amendment # 2 12/12/18, Amendment #3, 4/6/2020, Amendment #4 5/11/2020

[name],
[name]

For tissue from research only (optional) biopsy:

The research staff is to contact their respective pathology department point of contact (it is required to submit de-identified email chain with data to BrUOG), at least 24 hours prior to collection of a research only biopsy. Following the sites institutional policies & procedures, the specimen will be prepped, cassetted, processed, and embedded. The block will then be sectioned at 4µM, 20 sections and placed on charged slides. The tissue must be labeled with study number (BrUOG 355), patient initials, patient study number and time point. The tissue will then be sent for storage at the CRC for future testing.

Lifespan Clinical Research Center
[name],
[name],
[name]
[contact]

11 STUDY CALENDAR

Baseline evaluations are to be conducted within 28 days prior to start of protocol therapy, unless otherwise specified. Scans and x-rays must be done ≤4 weeks (28 days) prior to the start of therapy.

Assessments must be performed within 3 days prior to each treatment dosing day. Study assessments (required to be completed and resulted prior to any drug administration) and agents should be administered within ± 3 days of the protocol-specified date, unless otherwise noted.

The day an assessment (PE, labs, scan etc) is completed is day 0 for counting for example labs drawn on Friday can be used for Monday dosing as this is within 3 days

Baseline evaluations are to be conducted within 28 days prior to start of protocol therapy, unless otherwise specified below. Scans must be done <28 days prior to the start of therapy. Baseline labs are required within 14 days of registration. HCG is 7 days.						
Parameter	Pre- Study to be sent to BrUOG with results prior to registration	Weekly ^a within 3 days prior to dosing day 1 each week.	Monthly ^b required within 3 days prior to day 1 of each cycle	Off study (post completion of whole cycle) ^j +1 week	30 days post last treatment (+1 week) ^j	Follow-up
Informed consent(within 30 days of day 1) *pts are to be re-consented if ICF will be outside 30 day window	X					
Diagnostic pathology	X- no time frame					
FNA	X- no time					

BrUOG 355: 7/8/17, 7/11/17, 7/20/17, 8/7/17, 8/8/17, 8/14/17, 8/16/17, 8/21/17, 8/22/17, 8/24/17, 8/28/17, 9/5/17, 9/6/17, 9/8/17, 9/11/17, 11/7/17, 11/8/17, 11/19/17 approved DD, 11/20/17, 12/12/17, 12/14/17, 1/29/18, 2/1/18, 2/6/18, 2/7/18, 2/8/18, 2/9/18, 2/12/18, 2/13/18, 3/8/18 all reviews, 3/9/18, 3/13/18, 3/14/18, 3/15/18, 4/19/18, 4/23/18, 5/29/18, 6/5/18, Amendment # 1 7/9/18, Amendment # 2 12/12/18, Amendment #3, 4/6/2020, Amendment #4 5/11/2020

	frame k					
History & Physical	X	X	X	X	X	
Concurrent meds	X	X	X	X		
Toxicity Assessment	XD	X	X	X	X	
Vitals M	X	X	X	X		
Performance status	X	X	X	X		
Imaging evaluation(CT C/A/P preferred)	Xf			Xf	Xf	Xf
Tumor measurement	X			X		X
CBC (Including differential)	Xd	Xe	X	X		
Chemistries (CMP, CA/Mg/PO ₄)	Xd	X	X	X		
Amylase and lipase	Xd	X	X	X		
Liver Function tests (AST, ALT, Alk Phos, LDH)	Xd	X	X	X		
EKG	X					
Pregnancy test	Xg	Xg	Xg			
Audiogram	Xh		Xh	Xh		
Thyroid Function Tests (TSH, Free T4, T3)	X		X	X		
Viral studies (CD4 count – only required for patients who are HIV positive to certify eligibility, see exclusion 3.2.2 for timeframes and requirements.; HBsAg, , HCV Ab, if positive HCV Ab then order HCV RNA testing)	X					
Tumor Biopsy	X ^c					
Radiation			X ^N			
Cystoscopy, proctoscopy, barium enema	X- optional but if done must submit					

CMP=Glucose, Calcium, Albumin, Total Protein, Sodium, Potassium, CO₂, Chloride, BUN, Creatinine, ALP, ALT, AST, Bilirubin (total), amylase and lipase

- a. Obtain during cycles 1 and 2 Nivolumab (all cohorts) and chemoradiation therapy. Amylase and Lipase are required within 3 days of dosing with Nivolumab, with cycles 1 and 2 and q 2 weeks during chemoradiation therapy.
- b. Obtain for those patients receiving maintenance nivolumab treatment, prior to dosing each cycle

BrUOG 355: 7/8/17, 7/11/17, 7/20/17, 8/7/17, 8/8/17, 8/14/17, 8/16/17, 8/21/17, 8/22/17, 8/24/17, 8/28/17, 9/5/17, 9/6/17, 9/8/17, 9/11/17, 11/7/17, 11/8/17, 11/19/17 approved DD, 11/20/17, 12/12/17, 12/14/17, 1/29/18, 2/1/18, 2/6/18, 2/7/18, 2/8/18, 2/9/18, 2/12/18, 2/13/18, 3/8/18 all reviews, 3/9/18, 3/13/18, 3/14/18, 3/15/18, 4/19/18, 4/23/18, 5/29/18, 6/5/18, Amendment # 1 7/9/18, Amendment # 2 12/12/18, Amendment #3, 4/6/2020, Amendment #4 5/11/2020

- c. The first tumor biopsy may come from the diagnostic procedure where the diagnosis of cervical cancer was made. For patients who consent, a second biopsy should be attempted within 7 days after second dose of nivolumab in all patients, prior to chemoradiation.
- d. Must be obtained within 14 days prior to initiation of protocol treatment
- e. If grade 4 neutropenia is documented, monitor CBC twice weekly until resolved to \leq grade 3
- f. CT C/A/P is the preferred method of imaging. CT C/A/P must be obtained at the completion of chemoradiation (+ 14 days), 6 months later (+/- 14 days) and then q 6 months (+/- 14 days) for up to 3 years or until confirmation of PD. If an alternative imaging modality is used at baseline, the same imaging technique must be used throughout the study duration.
- g. Serum pregnancy test (women of childbearing potential) required within 7 days prior to day 1, Also required every 4 weeks (+/- 1 week) while on-study. Cycle 1 day 1: required HCG for all women of child bearing potential within 24 hours (1 day) prior to dosing day 1 cycle 1 only and confirmation of negative HCG test required to be sent to BrUOG. Patients with a positive test are required to be taken off study prior to any dosing on study.
- h. Required in all patients with a history of hearing loss. Must be obtained within 28 days prior to initiating protocol therapy. Repeat during treatment as clinically indicated.
- I. If screening labs are performed greater than 14 days prior to Cycle 1 Day 1, labs must be repeated on Cycle 1 Day 1 and must meet eligibility criteria. The patient may not start on study treatment until Cycle 1 Day 1 labs meet eligibility criteria. If screening labs are performed within 14 days prior to Cycle 1 Day 1, and meet eligibility criteria, labs do not need to be repeated on Cycle 1 Day 1 unless the investigator believes they are likely to have changed significantly. History, AE & concomitant medication assessment, vitals and performance status can be used from screening for cycle 1 day 1 if they were within the 14 day screening period (14 days from day 1). A physical exam within 7 days prior to cycle 1 day 1 can be utilized.
- j. Off-study evaluation to occur post completion of entire cycle. Follow-up visits or other contact are required in order to identify SAEs during the 30 days (+1 weeks) following the end of study treatment (Nivolumab, cisplatin or radiation), respectively. SAEs need to be reported after 30 days if the SAE is thought to be related to study treatment.
- k. patients who have positive or suspicious para-aortic nodes on lymphangiography, CT scan, or ultrasound examinations will undergo a fine needle aspiration (FNA), extraperitoneal lymph node biopsy, or laparoscopic sampling
- L. Survival and disease status will be collected approximately every 6 months (+/- 1 month) for 3 years. **DURING COVID 19, study follow-up may be done virtually if it is in the best interests for the patient and her safety. Virtual follow-up will be documented by the research team if performed.**
- M. Vital signs include: Weight, height (baseline only required), Blood pressure, heart rate, temperature, and Pulse oximetry oxygen saturation
- N Site to submit end of treatment Radiation Oncology note summarizing all treatment

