If Nivolumab is discontinued, the patient is to be taken off study. The total treatment patient BrUOG 355: 7/8/17, 7/11/17, 7/20/17, 8/7/17, 8/8/17, 8/14/17, 8/16/17, 8/21/17, 8/22/17, 8/24/17, 8/28/17, 9/5/17, 9/6/17, 9/8/17, 9/11/17, 11/7/17, 11/8/17, 11/19/17 approved DD, 11/20/17, 12/12/17, 12/14/17, 1/29/18, 2/1/18, 2/6/18, 2/7/18, 2/8/18, 2/9/18, 2/12/18, 2/13/18, 3/8/18 all reviews, 3/9/18, 3/13/18, 3/14/18, 3/15/18, 4/19/18, 4/23/18, 5/29/18, 6/5/18, Amendment # 1 7/9/18, Amendment # 2 12/12/18, Amendment #3, 4/6/2020, Amendment #4 5/11/2020

received will be collected, but once patient is off study, all treatment is per standard of care and does not need to follow-BrUOG 355.

In situations when RT is not given (held for toxicity or other reasons (weather, machine is down, holiday), cisplatin and Nivolumab should not be given and should also be held.

If Nivolumab is held on a day Cisplatin is due and the patient meets criteria to receive Cisplatin and Radiation then every attempt should be made to administer Cisplatin and radiation, while holding Nivolumab.

Every attempt should be made for all patients to complete radiation therapy (even if cisplatin and nivolumab are held)

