16.1.1. Safety review

A safety review for each cohort will be conducted. For cohort 1, safety analysis will occur at the end of chemoradiation. For patients in cohort 2 (who receive nivolumab following chemoradiation), evaluation for safety will occur 4 weeks following initiation of maintenance nivolumab. For patients in cohort 3, safety analyses will occur at the end of chemoradiation and after maintenance therapy has completed.

Criteria that will determine safety will include:

- Grade 3 or higher adverse events that persists for 14 days or longer despite dose-holds and/or maximal medical support. This excludes uncomplicated neutropenia and any laboratory abnormalities deemed by the treating clinician as having no clinical significance
- Inability to complete chemoradiation within 8 weeks

The BrUOG overall PI, the Women & Infants' Hospital site PI (once study is activated), and the Medical Director of BrUOG will review safety data as described to make determinations of feasibility. Enrollment to cohort 2 will not be dependent on the safety review for cohort 1. However, the safety review will be completed for cohort 2, before enrollment begins in cohort 3.

If more than 25% of patients (more than 2 patients in cohort 1 or more than 1 patient in cohort 2) experience a grade 3 or higher adverse event that persists for 14 days or longer, despite dose-holds and/or maximal support, the treatment will be considered not feasible and the next cohort will not be opened.

If more than 25% of patients (more than 2 patients in cohort 1 or more than 1 patient in cohort 2) are unable to complete chemoradiation within 8 weeks, the treatment will be considered not feasible and the next cohort will not be opened.

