16.4 Analysis of Primary Endpoints

Time-to-event endpoint of progression free survival at 3 years will be described using the method of Kaplan-Meier, and presented with 90% confidence intervals. Patients that are alive without disease progression at time of analysis are censored at the date of last disease evaluation. Acute Treatment-related toxicities that occur during and within six months of study treatment will be summarized by maximum grade and by term using CTCAE v4.0 and reported with 90% binomial exact confidence intervals. Acute toxicities will be used to determine the feasibility within each cohort.

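### As the calendar is written, no routine thyroid test falls between baseline and the off-study visit (cohort 1) or the first maintenance dose (cohorts 2 and 3), a gap of roughly 10 to 17 weeks

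*Combined protocol and SAP*

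**What the plan says.** The calendar row "Thyroid Function Tests (TSH, Free T4, T3" carries marks under Pre-study, Monthly and Off study. The Weekly, 30-day and Follow-up cells are empty.

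The footnotes say when each column applies. Footnote a on Weekly reads "Obtain during cycles 1 and 2 Nivolumab (all cohorts) and chemoradiation therapy". Footnote b on Monthly reads "Obtain for those patients receiving maintenance nivolumab treatment, prior to dosing each cycle". Blood counts, chemistries, liver tests and amylase/lipase are all marked Weekly. Section 11 also requires assessments within 3 days before each dosing day, but the column marks decide which assessments those are. No other section schedules a thyroid test.

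Section 8.1 lists endocrinopathies among the select adverse events for nivolumab. Section 5.5.1 requires permanent discontinuation for Grade 4 drug-related endocrinopathy. Section 16.1 makes acute toxicity of nivolumab with chemoradiation the primary endpoint, and section 16.4 will summarise "Acute Treatment-related toxicities that occur during and within six months of study treatment" by maximum grade and term, so low-grade events count.

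**The concern.** The period without a scheduled thyroid test is the period the trial was set up to study: induction nivolumab followed by chemoradiation, with concurrent nivolumab in cohorts 1 and 3. The protocol tests before every 480 mg maintenance dose given 4-weekly. It does not test during 240 mg dosing every 2 weeks, which delivers the same amount per 4 weeks (2 x 240 = 480 mg).

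Two things are at stake. A silent thyroid event that persists is recognised later than it need be. A silent event that resolves before the first post-baseline test is never recorded, so the all-grade acute-toxicity counts may be incomplete.

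**Working it through.** The plan states no interval to the first post-baseline thyroid test, so it has to be derived.

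**Inputs**
- Two induction doses 2 weeks apart: days 0 and 14 (5.3).
- Chemoradiation starts 14 days (+/- 7) after the second dose: nominally day 28, week 4 (5.4).
- Planned duration about 6 weeks, 42 days (5.6). Upper limit 60 days in 5.7, 6 weeks in 5.7.5, and 8 weeks as the feasibility criterion in 16.1.1. Section 5.7.3 accepts up to 66 days as a variation.
- Off-study visit has a +1-week window (section 11).
- Maintenance starts 2-3 weeks after chemoradiation in cohort 2 and no more than 4 weeks after it in cohort 3 (5.4).

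**Weeks from first nivolumab dose to first post-baseline thyroid test (nominal start, 60-day limit)**
- Cohort 1: (28+42)/7 = 10.0 to (28+60+7)/7 = 13.6.
- Cohort 2: (28+42+14)/7 = 12.0 to (28+60+21)/7 = 15.6.
- Cohort 3: (28+42)/7 = 10.0 to (28+60+28)/7 = 16.6.

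**Upper end in weeks, by the radiation limit applied**

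| Limit | Cohort 1 | Cohort 2 | Cohort 3 |
|---|---|---|---|
| 6 weeks | 11.0 | 13.0 | 14.0 |
| 8 weeks | 13.0 | 15.0 | 16.0 |
| 60 days | 13.6 | 15.6 | 16.6 |
| 66 days | 14.4 | 16.4 | 17.4 |

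The windows widen these further. Allow the second dose +/- 3 days, chemoradiation start +/- 7 days and labs up to 3 days before a maintenance dose. With the 60-day limit the ranges become about 8.6-15.0, 10.1-17.0 and 8.1-18.0 weeks.

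Two alternative readings stay inside the nominal ranges. If cohort 1's off-study visit is counted from the end of the last concurrent 2-week cycle, it falls at (28+28+14)/7 = 10.0 to 11.0 weeks. If cohort 3 starts maintenance at 2-3 weeks, as cohort 2 does, its range is 12.0-15.6 weeks.

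**Doses given before any scheduled post-baseline result**
- Per completing patient, after the first dose: cohorts 1 and 3, 1 induction + 3 concurrent = 4; cohort 2, 1 induction.
- All patients: 8x4 + 4x1 + 12x4 = 84.
- Planned doses, with 104/4 = 26 maintenance doses: 8x5 + 4x28 + 12x31 = 524. Less 24 first doses, this leaves 500. 84/500 = 16.8%.
- With tests at weeks 4 and 8, only the second induction dose precedes a result: 24/500 = 4.8%.
- Cohorts 1 and 3 fall from 80 to 20 doses. Cohort 2 stays at 4.

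**Gaps with tests at weeks 4 and 8 (nominal start, 60-day limit)**
- First dose to week 4, then week 4 to week 8: 4 weeks each.
- Week 8 to the next test: cohort 1, 2 to 13.6-8 = 5.6 weeks; cohort 2, 4 to 15.6-8 = 7.6; cohort 3, 2 to 16.6-8 = 8.6.
- The last concurrent dose falls on day 29 (week 8), so cohorts 2 and 3 receive no nivolumab between that draw and maintenance. The pre-maintenance test must be resulted before dosing.

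**The case against.** **It may be a labelling fault.** Footnote b cannot be literally right for every row. Radiation is marked only under Monthly, yet none is given in maintenance. Audiogram is marked Monthly but not Weekly, although cisplatin is given only during chemoradiation. If Monthly was meant throughout treatment, the gap disappears. This is a fair reading of intent, but footnote b does not say it, and sites could read the calendar either way. The text would still need amending.

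**The ranges are soft.** They are: the upper ends depend on which of the protocol's conflicting radiation limits applies. Even under the shortest, the first test comes up to 11-14 weeks after the first dose.

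**The dose count measures process, not harm.** This stands. The endocrine algorithm figure in Appendix D is not shown, so it is not known whether a silent result would change dosing. In cohort 2 the count does not move.

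**Other monitoring continues.** Weekly history, examination, vitals and toxicity checks can find symptomatic events, and suspected immune toxicity requires nivolumab to be held. Patients removed early are tested sooner, since "If Nivolumab is discontinued, the patient is to be taken off study" and an off-study thyroid test follows. This is a partial backstop. Fatigue is listed as very common with nivolumab (8.1), section 8.2 bars questioning about specific events, and a silent event prompts nothing.

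**Section 8.1 sets no test frequency.** Correct. The 4-weekly interval is taken from the protocol's own maintenance schedule.

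**Conclusion.** The gap is real on the text, and closing it is a modest improvement in monitoring and ascertainment. For completing patients the first post-baseline thyroid test comes roughly 10-14, 12-16 and 10-17 weeks after the first dose in cohorts 1, 2 and 3 (upper ends 11, 13 and 14 under the 6-week limit). The conclusion assumes that the calendar marks and footnotes mean what they say, and that patients complete chemoradiation. The dose counts also assume full enrolment and 26 maintenance doses.

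Three stronger readings are tempting, and the documents do not support them.
- A reader might infer that thyroid toxicity goes uncounted. Persistent events are still found at the first later test, which for completing patients falls within the acute window of either 16.1 or 16.4. The loss is silent events that resolve first, plus later recognition of the rest.
- A reader might infer that the feasibility decision is compromised. It needs Grade 3 or higher events lasting 14 days and excludes "any laboratory abnormalities deemed by the treating clinician as having no clinical significance".
- A reader might infer that cohort 3's review is undermined, because "For patients in cohort 3, safety analyses will occur at the end of chemoradiation and after maintenance therapy has completed" and its first test may come up to 4 weeks after chemoradiation ends. Section 16.1.1 sets numerical limits only for cohorts 1 and 2, and no cohort follows cohort 3, so this carries little weight.

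The number of missed events is unknown. Section 8.1 lists hypothyroidism as an uncommon serious event with monotherapy (1/1,000 to under 1/100). That is 24x0.001 = 0.024 to 24x0.01 = 0.24 serious events in 24 patients. The events at issue here are nonserious, and the documents give no rate for those.

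**What to change.** Mark thyroid tests in the Weekly column, with a footnote requiring them every 4 weeks through induction and chemoradiation: with the labs before chemoradiation day 1 (about week 4) and at chemoradiation day 29 (about week 8). The calendar already handles less-than-weekly tests in that column: footnote a sets amylase/lipase at 2-weekly during chemoradiation, and footnote g's pregnancy test is "Also required every 4 weeks (+/- 1 week) while on-study", which serves as a wording model. If Monthly was meant to apply throughout treatment, amend footnote b to say so instead.

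The cost is one calendar mark, one footnote and 24x2 = 48 panels, all on draws already scheduled. The downside is some extra low-grade laboratory findings.

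A draw at the end of chemoradiation in cohorts 2 and 3 (4+12 = 16 panels, possibly needing their own blood draw) is optional and not part of the core fix.
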